2.1 Data analysis general information

Patients who discontinue study drug will be considered withdrawn from the study after the final visit assessments and the final safety follow-up visit are performed or when it is clear that the patient will not return for final visit assessments and/or final safety follow-up visit.

The analysis of the core phase, including the primary and key secondary analyses was performed based on cumulative data collected up to the date when all enrolled patients had either completed or prematurely withdrawn from the core phase of study. The results and outcomes of this analysis were presented in an interim CSR.

The study was powered based on the primary and key secondary analyses. All efficacy analyses presented in the Final CSR are considered as supportive, and no formal statistical testing will be performed.

Analysis for the Final CSR will be performed once all patients have either completed the extension period or discontinued earlier.

Data will be analyzed using the SAS System for data analysis V9.4 or higher.

2.1.1 General definitions

2.1.1.1 Study day

Study Day 1 is the date of first administration of study drug.

The study day for an event that occurred prior to study day 1 will be calculated as (date of event – date of first administration of study drug).

The study day for an event that occurred after study day 1 will be calculated as (date of event – date of first administration of study drug) +1.

Study day will be displayed in the data listings.

2.1.1.2 Baseline

For efficacy and safety evaluations (e.g. laboratory assessments and vital signs): the last available pre-dose assessment within 35 days prior to or on Study Day 1 (before the first dose of LCI699) is taken as the “baseline” assessment; the last available assessment within 21 days prior to the first dose of randomized treatment (LCI699 or Placebo) is taken as the “randomization” assessment; If patients have no value as defined above, the baseline/randomization result will be considered missing.

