5.2 Inclusion criteria

Patients must fulfill all of the following criteria to be eligible for inclusion in this study:

1. Written informed consent must be obtained before any assessment is performed.
2. Male or female patients aged 18 - 75 years
3. Patients must have confirmed Cushing's disease that is persistent or recurrent as evidenced by:
 - a. mUFC > 1.5 x ULN at screening (the mean of three 24-hour urine samples collected during screening, after completion of the washout period (if applicable), confirmed by the central laboratory and available at Day 1)
 - b. Morning plasma ACTH above lower limit of normal
 - c. Confirmation of pituitary source of excess ACTH is defined by any of the following three criteria:
 1. MRI confirmation of pituitary adenoma > 6 mm; OR
 2. bilateral inferior petrosal sinus sampling (BIPSS) with either CRH or DDAVP stimulation for patients with a tumor \leq 6mm. The criteria for a confirmatory BIPSS test are any of the following:
 - Pre-dose central to peripheral ACTH gradient > 2;
 - Post-dose central to peripheral ACTH gradient > 3 after either CRH or DDAVP stimulation
 3. histopathologic confirmation of an ACTH-staining adenoma in patients who have had prior pituitary surgery.
4. Patients with a history of prior pituitary surgery must be at least 30 days post-surgery to be eligible for inclusion in this study.

5. Patients that received glucocorticoid replacement therapy post-operatively must have discontinued such therapy for at least one week, or (5 half-lives), whichever is longer, prior to screening.
6. Patients with de novo Cushing's disease can be included only if they are not considered candidates for surgery (e.g., poor surgical candidates, surgically unapproachable tumors, patients who refuse to have surgical treatment, or surgical treatment is not available)
7. Patients with a history of pituitary irradiation can be included, provided that at least 2 years (stereotactic radiosurgery) or 3 years (conventional radiation) have elapsed from the time of last radiation treatment to the time of enrollment into this study.
8. Patients are permitted to washout current drug therapy to meet these entry criteria if they have a known diagnosis of Cushing's disease. Rescreening can be used as needed to ensure washout is complete. The following washout periods must be completed before baseline efficacy assessments are performed:
 - a. Steroidogenesis inhibitors (ketoconazole, metyrapone): 1 week

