7.1.1 Screening

Written main informed consent must be obtained before any study specific assessments are performed.

The screening assessments must be performed within 35 days before planned patient's eligibility confirmation and before the start of the first study drug dose of LCI699 at day 1.

For patients who are on a medication requiring a >4 week washout, consideration can be given to switching them to a medication with a shorter washout (1 week) until the last part of the washout.

Based on the central laboratory turnaround time, it is highly recommended to send the three 24-hour Urinary Free Cortisol samples to the central Laboratory at least 14 days prior to day 1 in order to ensure that sufficient time is allowed for central laboratory results to become available.

Eligibility is assessed based on the screening results only collected at the screening visit, unless specified otherwise as per the Inclusion/Exclusion criteria. For details, refer to [Section 5.2](#) and [Section 5.3](#).

For laboratory evaluations used to determine eligibility, a repeated evaluation within the screening window is permitted for screening results out of the defined range. If the repeated laboratory result meets the criteria, that result may be used to determine eligibility. If the repeated laboratory result does not meet the criteria, the patient will be considered a screening failure. In this case, the patient will not be required to sign another ICF.

A new ICF will need to be signed if the investigator chooses to re-screen the patient after a patient has screen failed. The rescreening should be documented in the source files and re-registered in IRT using the same Patient Number.

If the rescreening occurs within 60 days of the end of the original screening period, the following procedures do not have to be repeated: pituitary MRI, photography and DXA scan and all other assessments must be repeated.

If the rescreening occurs more than 60 days after the end of the original screening period, all assessments must be repeated.

An individual patient may only be rescreened once for the study. Once the number of patients screened and enrolled is likely to ensure target enrollment, the Sponsor may close the study to further screening. In this case the patients who screen failed will not be permitted to re-screen. For details of assessments, refer to [Table 7-1](#).

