2.7 Analysis of secondary efficacy objectives

For the objectives identified below, the definition of Baseline/Randomization assessment and the method of computing confidence intervals are specified in Section [2.1.1.2](#) and Section [2.1.1.8](#) respectively. Last observation carried forward (LOCF) method will not be used in any of these analyses. For analysis using FAS, results will be presented by LCI699 group, Placebo group, Non-randomized patients, and All patients.

2.7.1 Compare the time-to-last control of mUFC during the randomized withdrawal period between patients randomized to continued LCI699 and placebo

The results of this objective were reported in the interim CSR, and will not be repeated for the Final CSR.

2.7.2 Assess the complete, partial, and overall response rate at Week 12, Week 24, Week 48, and during the extension period

The proportion of complete responders (enrolled patients with $mUFC \leq ULN$), partial responders (enrolled patients with $mUFC > ULN$ and at least 50% reduction from baseline), and overall responders (enrolled patients with $mUFC \leq ULN$ or have at least 50% reduction from baseline) will be summarized using point estimates for every scheduled visit in the core and extension (provided [adequate follow-up](#)) at which UFC is collected. 95% 2-sided CIs for response rates will be provided for Week 48, Week 60, Week 72 and the last available assessment of the study. The FAS will be used for the analyses.

2.7.3 Assess the change in mUFC during the core and extension period of study

For the actual value and change in mUFC from baseline during the overall study period, descriptive summaries will be provided for every scheduled visit in the core and extension (provided [adequate follow-up](#)) at which UFC is collected. The FAS will be used for the analysis.

Patients randomized to placebo during the RW period, will not have their mUFC values included in the analysis for visits at which they received placebo.

2.7.4 Assess the change in cardiovascular-related metabolic parameters associated with Cushing's disease during the core and extension period of the study

The following parameters will be analyzed: glucose, HbA1c, fasting lipid profile, SBP, DBP, weight, waist circumference and BMI).

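### The SAP's 35-day baseline window has no imaging exception, so rescreened patients whose reused MRI, photographs or DXA are older than 35 days on Day 1 lose that baseline

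*SAP*

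**What the plan says.** **The SAP rule.** SAP 2.1.1.2 opens with its scope, "For efficacy and safety evaluations (e.g. laboratory assessments and vital signs"), so laboratory tests and vital signs are examples and not the limit of the rule. Baseline is "the last available pre-dose assessment within 35 days prior to or on Study Day 1 (before the first dose of LCI699"). The section ends: "If patients have no value as defined above, the baseline/randomization result will be considered missing".

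**Where it applies.** SAP 2.7 extends the rule to its own analyses: "For the objectives identified below, the definition of Baseline/Randomization assessment and the method of computing confidence intervals are specified in Section" (the references there are to 2.1.1.2 and 2.1.1.8). Those objectives include photography (2.7.5) and bone mineral density by DXA (2.7.6). Tumor volume (2.8.4.3) stands in the safety section, so the general scope of 2.1.1.2 reaches it too.

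**The protocol rule.** Protocol 7.1.1 states: "If the rescreening occurs within 60 days of the end of the original screening period, the following procedures do not have to be repeated". The list that follows is "pituitary MRI, photography and DXA scan and all other assessments must be repeated". Beyond 60 days everything is repeated. Protocol 5.2, criterion 8, gives one purpose of the provision: "Rescreening can be used as needed to ensure washout is complete".

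Neither document says that a retained image counts as baseline despite its age.

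**The concern.** One document lets a site keep an image, and the other discards it as too old. A site can comply fully with Protocol 7.1.1 and the patient still ends up with no baseline in the analysis, because no second image need exist.

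The tumor data matter most. Protocol 2.7 names corticotroph tumor progression as a potential risk, and Protocol 8.1.3 makes pituitary tumor enlargement a group of adverse events of special interest. SAP 2.8.4.3 restricts the volume summary to patients with detectable tumor at baseline, and reports invasiveness and measurable-tumor status as changes from baseline. A patient whose baseline is set to missing leaves the volume summary and both change-in-status results, although a scan exists. The photography shift tables and the bone density change are lost in the same way.

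**Working it through.** The plan gives no figure on this point, so there is none to reproduce. The check is date arithmetic.

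**Inputs**
- *a*: days from the image to the end of the original screening period. Not stated. Assumed range 0 to 35, or 0 to 7 if the image was taken in the Visit 2 week just before that period ended.
- *g*: days from the end of the original screening to the start of rescreening, 0 to 60 (Protocol 7.1.1, reading the 60 days as running to the start of rescreening).
- *s*: days from the start of rescreening to Day 1, 8 to 35 (Visit 1 is Day -35 to Day -8; Protocol Table 7-1, SAP Table 2-1). It is at least 14 if the site follows the advice in Protocol 7.1.1 on sending the screening urine samples.
- Limit: 35 days (SAP 2.1.1.2).

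**Formula.** Age of a reused image on Day 1 = *a* + *g* + *s*. Baseline survives only if this is 35 or less.

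**Results**
- Most favorable case, *a* = 0 and *s* = 8: *g* can be at most 35 − 8 = 27. At *g* = 28 the age is 0 + 28 + 8 = 36, so every gap from 28 to 60 days breaks the window. At *g* = 60 the youngest possible image is 68 days old.
- With *s* = 14: *g* can be at most 35 − 14 = 21.
- Shorter gaps can fail too. For example, *a* = 7, *g* = 7, *s* = 25 gives 39.
- Oldest permitted image: 35 + 60 + 35 = 130 days, or 7 + 60 + 35 = 102 days if *a* is at most 7.
- Share of the 60-day range that always fails: (60 − 27)/60 = 55%, or (60 − 21)/60 = 65% with the 14-day advice. These are shares of a calendar range, not of patients.
- Illustration only, counting every whole-day combination of *g* (0 to 60) and *s* (8 to 35) equally, 61 × 28 = 1,708 combinations for each value of *a*. With *a* = 0, 406 stay within 35 days, so 76% fail. With *a* from 0 to 7, 2,520 of 13,664 stay within, so 82% fail. With *a* from 0 to 35, 4,060 of 61,488 stay within, so 93% fail.

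**Which images can properly serve as baseline.** Inclusion criterion 8 requires washout to be complete before baseline efficacy assessments. Protocol 7.2.1 classes photography and DXA as efficacy assessments; pituitary MRI is under safety, in 7.2.2.5. If a patient was rescreened because washout was incomplete, photographs or DXA from the original screening may predate its completion and then conflict with criterion 8. The MRI does not have this difficulty.

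**The case against.** The strongest reply is that few patients can be exposed. Protocol Table 7-1 schedules MRI, photography and DXA at Visit 2 (Day -7 to Day -1), while eligibility rests mainly on the screening visit. A patient who fails at Visit 1 normally has no image to carry over. Repetition is also optional, so some rescreened patients will have fresh images. Both points stand and limit the size. They do not remove the conflict, since the protocol expressly provides for reuse.

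The consequence is also limited. Urinary cortisol must be repeated at rescreening, and SAP 2.1 describes all efficacy analyses in the final report as supportive, without formal testing. That stands.

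It can also be said that a recency limit is reasonable for photography, because the protocol itself rates physical features as early as Week 12. That is fair, and it is a reason not to assume that all three measures are stable over the permitted interval. The documents offer no support for such an assumption.

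A reader might infer more than the documents support:
- *That every affected patient loses all three endpoints.* DXA is not done in Germany (Protocol 7.2.1.3), photography may be omitted for cultural reasons (7.2.1.2), and the volume summary covers only patients with detectable tumor. Invasiveness and measurable-tumor status at each visit are still reported; only the change is lost.
- *That sites were told not to repeat the images.* The protocol only says that they need not.
- *That the loss falls selectively on patients with prior medical therapy.* Amendment 2 did introduce rescreening for long washouts, but no counts or reasons are given. The longest washout, 6 months for mitotane, would often exceed the 60-day limit, after which everything is repeated.

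**Conclusion.** Wrong as written. SAP 2.1.1.2 and Protocol 7.1.1 conflict for a rescreened patient whose reused image is more than 35 days old on Day 1. That is certain for gaps of 28 to 60 days and possible for shorter ones. Patients with repeated images, or with a reused image of 35 days or less, keep their baseline.

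The number affected cannot be derived. The documents give 137 treated patients (Amendment 4 rationale) but no count of those rescreened, and it may be small. The loss is confined to descriptive summaries and does not touch the primary or key secondary endpoint. It still deserves correction, because one of those summaries tracks tumor growth.

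The 28-day threshold rests on Visit 1 of rescreening being at least 8 days before Day 1 and on measuring the gap to the start of rescreening. This SAP serves the final report; the separate core-phase SAP is not among the documents, so its baseline rule could not be checked.

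**What to change.** Amend SAP 2.1.1.2 along these lines:

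> For pituitary MRI or CT, baseline is the last assessment before the first dose of LCI699, including one retained from the original screening under Protocol 7.1.1. The same applies to DXA and photography, provided that the retained assessment was made after any washout required by inclusion criterion 8 was complete; otherwise it is listed and flagged. The 35-day window applies to all other measures.

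Add a footnote to the tumor, photography and bone density tables with the number of patients whose baseline is older than 35 days. If there are none, the footnote says zero and the matter is closed.

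The cost is a short SAP change, separate baseline programming for these three assessments, and a comparison of image dates with the stop dates of prior therapy, which Protocol 6.4 already asks sites to record. No new data are needed. The downside is an older baseline in a few patients, which the footnote discloses.

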2.1.1.3 Visit number

The time point (Day/Month) associated with an assessment will be determined by the visit number assigned to the assessment in the database. The mapping of visit numbers to time points in the core study and the extension study are provided in the table below.

Table 2-1 Scheduled visits in core phase

Core study Visit	Day/Week	Clarifying Notes
Visit 1	Day -35 to Day -8	Screening
Visit 2	Day -7 to Day -1	Baseline
Visit 3	Day 1/Week 0	Dose escalation period
Visit 4	Day 15/Week 2	Dose escalation period
Visit 5	Day 29/Week 4	Dose escalation period
Visit 6	Day 43/Week 6	Dose escalation period
Visit 7	Day 57/Week 8	Dose escalation period
Visit 8	Day 71/Week 10	Dose escalation period
Visit 9	Day 85/Week 12	Dose escalation period
Visit 10	Day 113/Week 16	Treatment period
Visit 11	Day 141/Week 20	Treatment period
Visit 12	Day 169/Week 24	Treatment period
Visit 13	Day 183/Week 26	Randomized Withdrawal period
Visit 14	Day 197/Week 28	Randomized withdrawal period
Visit 15	Day 211/Week 30	Randomized withdrawal period
Visit 16	Day 225/Week 32	Randomized withdrawal period
Visit 17	Day 239/Week 34	Randomized withdrawal period

Core study Visit	Day/Week	Clarifying Notes
Visit 1	Day -35 to Day -8	Screening
Visit 18	Day 253/Week 36	Open Label period
Visit 19	Day 281/Week 40	Open Label period
Visit 20	Day 309/Week 44	Open Label period

Table 2-2 Scheduled visits in extension period

Extension study Visit	Day/Week	Clarifying Notes
Visit 21	Day 337/Week 48	Extension
Visit 22	Day 365/Week 52	Extension
Visit 23	Day 393/Week 56	Extension
Visit 24	Day 421/Week 60	Extension
Visit 25	Day 449/Week 64	Extension
Visit 26	Day 477/Week 68	Extension
Visit 27	Day 505/Week 72	Extension
Visit 28	Day 589/Week 84	Extension
Visit 29	Day 673/Week 96	Extension
Visit 30	Day 757/Week 108	Extension
Visit 31	Day 841/Week 120	Extension
.....	Every 84 days/12 weeks	Extension

Unlike the above visits that are scheduled to occur after a fixed number of days have elapsed since Day 1, the Visits 777 (End-of-Treatment in core phase) and 778 (End-of-Treatment in extension period) are scheduled when the patient either completes the respective study period or decides (or is mandated by the protocol) to prematurely discontinue from the study.

If such a visit happens neither too soon nor too late after the actual last scheduled visit (LASTVIS) prior to the 777/778 visit, then it will be mapped to the next scheduled visit (LASTVIS+1) in the visit schedule (from the tables above).

The 777/778 visit will be considered to have occurred neither too soon nor too late after the actual last scheduled visit if the number of days between the two visits is

- (i) at least half of the planned gap between the patient’s actual last scheduled visit (LASTVIS) and the next scheduled visit and
- (ii) at most the total of (a) the planned gap between the patient’s actual last scheduled visit (LASTVIS) and the next scheduled visit and (b) half of the planned gap between the patient’s next two scheduled visits.

If the number of days between the 777/778 visit and LASTVIS is less than the range specified above then the 777/778 visit will be mapped to an unscheduled visit of LASTVIS; if it is more then it will be mapped to an unscheduled visit of LASTVIS + 1.

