7.1.4 End of treatment visit including study completion and premature withdrawal

Patients who discontinue study treatment before visit 777 (if patient is in the core phase of the study) or 778 (if patient is in the extension phase of the study), should be scheduled for a visit as soon as possible, at which time all of the assessments listed for the EOT visit will be performed ([Table 7-1](#), [Table 7-3](#) or [Table 7-5](#)) with the following exceptions:

- Patients discontinuing treatment prior to the Week 36 visit do not need to have an EOT core DXA scan

- Patients discontinuing prior to the Week 12 visit or between the Week 24 and Week 36 visits do not need to have an EOT core pituitary MRI (or CT) (i.e. scans are needed if patients discontinue within the 12 week period prior to the Week 24 and Week 48 visits).
- Patients discontinuing or completing extension phase within 36 weeks since their last pituitary MRI (or CT) or DXA scan do not need to have an EOT extension pituitary MRI (or CT) or DXA scans.

An End of Treatment Phase Disposition CRF page should be completed, giving the date and reason for stopping the study treatment. At a minimum, all patients who discontinue study treatment, including those who refuse to return for a final visit, will be contacted for safety evaluations during the 30 days following the last dose of study treatment (Visit 779).

If a patient withdraws or discontinues from the study prematurely, an unscheduled PK sample should be taken, and the sample should be recorded in the “Unscheduled PK” CRF page.

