2.1.1.7 Calculation of proportions of responders

All enrolled patients will be included in the analysis for calculating the proportion of responders at time points up to Week 48.

For calculation of proportion of responders beyond Week 48 (e.g. a time point in extension period), the following rules will be applied to determine whether patients are included in the analysis.

1) patients who declined to enter optional extension period after completion of the core phase will always be excluded.

2) patients who discontinued prior to the data cutoff date for the Final DBL will be included up to the furthest scheduled visit they could have completed if they had not discontinued early based on data cut off and last completed based on the date of last completed schedule visit and analyses cut-off date. For example, if the last completed scheduled visit for an early discontinued patient is Week 52, and the time between data cutoff and last completed scheduled visit is 8 weeks, he/she will be included in the analyses up to Week 60.

If included in the analysis for calculating the proportion of responders at a given timepoint, patients who discontinued before this timepoint will be counted as non-responders.

Patients randomized to placebo during the RW period, will not be included in the denominator for visits at which they received placebo.

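### The SAP rule for placing Visit 777 files a core completer's Week 48 results under Week 44 whenever the Week 44 visit was skipped

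*SAP*

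**What the plan says.** SAP 2.1.1.3 takes the time point of an assessment from its visit number. Visits 777 and 778, the end-of-treatment visits of the core and extension, have no fixed day there. They occur when a patient completes the period or stops early, and both kinds of patient fall under one rule:

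- The condition is "If such a visit happens neither too soon nor too late after the actual last scheduled visit (LASTVIS) prior to the 777/778 visit", and the consequence is "then it will be mapped to the next scheduled visit (LASTVIS+1) in the visit schedule".
- The lower limit is "at least half of the planned gap between the patient’s actual last scheduled visit (LASTVIS) and the next scheduled visit".
- The upper limit is that planned gap plus "half of the planned gap between the patient’s next two scheduled visits".
- If the interval is too short, the visit becomes an unscheduled visit of LASTVIS. For one that is too long, "if it is more then it will be mapped to an unscheduled visit of LASTVIS + 1".

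SAP Table 2-1 (core) ends at Visit 20, Week 44. Week 48 appears only in Table 2-2, as Visit 21 of the extension.

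Protocol Tables 7-2 and 7-3 put the Week 48 efficacy, imaging and questionnaire assessments in the Visit 777 column (Day 337). Visit 21 in Protocol Table 7-4, also Day 337, has only consent, IRT and a 12-lead ECG. The first UFC collection in the extension table is at Week 60.

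On response rates, SAP 2.1.1.7 states: "All enrolled patients will be included in the analysis for calculating the proportion of responders at time points up to Week 48". SAP 2.7 rules out last observation carried forward. SAP 2.7.2 plans a 95% CI at Week 48, Week 60, Week 72 and the last available assessment.

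**The concern.** The rule measures from the previous attended visit rather than from Day 1. That is reasonable for a patient who stops early, because the end-of-treatment visit can then fall on any day. A core completer is different: Visit 777 is the Week 48 visit, with a planned study day. For that patient the rule lets attendance at Week 44 decide whether an on-time Week 48 measurement counts as Week 48.

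The stake is the Week 48 column of the Final CSR: response rate with CI, mUFC, cardiovascular-related parameters, photography, bone density, tumour volume and questionnaires. For the response rate the error runs one way. A controlled patient stays in the denominator and leaves the numerator.

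**Working it through.** **Inputs**

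- Planned days (SAP Tables 2-1 and 2-2): Week 36 = Day 253, Week 40 = Day 281 ("Day 281/Week 40"), Week 44 = Day 309, Week 48 = Day 337, Week 52 = Day 365.
- Visit window: ±3 days (Protocol 7.1.3).
- Enrolled and treated: 137 (Protocol, Amendment 4 rationale).
- LASTVIS is read as the last scheduled visit attended, because counting days between two visits needs an actual date.

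**Planned days reproduced.** Day = 7 × week + 1 gives 7 × 40 + 1 = 281, 7 × 44 + 1 = 309 and 7 × 48 + 1 = 337, as tabulated.

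**Window.** Let g1 be the planned gap from LASTVIS to the next visit, and g2 the gap after that. The accepted interval is g1/2 to g1 + g2/2. All gaps here are 28 days, so it is 14 to 28 + 14 = 42 days.

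| Last visit attended | Days to Day 337 | Range with ±3 days on both visits | Result |
|---|---|---|---|
| Week 44 (Day 309) | 28 | 22 to 34 | within 14 to 42: Week 48 |
| Week 40 (Day 281) | 56 | 50 to 62 | above 42: unscheduled Week 44 |
| Week 36 (Day 253) | 84 | 78 to 90 | above 42: unscheduled Week 40 |

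The rule works when Week 44 was attended and fails on every permitted combination of dates when it was not. A wider window would not help. The only available targets are LASTVIS and LASTVIS + 1, so from Week 40 the rule cannot reach Week 48 at all.

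**Effect on the Week 48 response rate.** Each affected patient in control removes one responder from a denominator of 137:

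- 1 patient: 1/137 = 0.73 points
- 3 patients: 3/137 = 2.19 points
- 5 patients: 5/137 = 3.65 points

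The counts of 3 and 5 are illustrations. The documents do not report how many patients skipped Week 44.

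**The case against.** The strongest reply is that the trigger is narrow and the consequence limited. Week 44 must be skipped altogether; a late Week 44 visit keeps its visit number. Study drug is supplied to last until at least the next scheduled visit (Protocol Table 6-3), so missing a visit and still completing on treatment is probably not common. SAP 2.1 calls all Final CSR efficacy analyses supportive, with no formal testing. If the Week 48 rate were between 50% and 80% (assumed), the approximate CI half-width would be 1.96 × √(0.5 × 0.5/137) = 8.4 to 1.96 × √(0.8 × 0.2/137) = 6.7 points, so a few misfiled patients would lie inside the reported uncertainty. All of this stands and limits the point's importance. It does not make the mapping correct.

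Four stronger readings are tempting, and the documents do not support them:

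- **All Week 48 data are lost.** They leave the Week 48 by-visit summaries only. Listings and worst post-baseline tables keep them, as do last post-baseline tables and the last available assessment where nothing later exists. The Visit 21 ECG of extension entrants is unaffected.
- **The SAP declares such a patient a non-responder.** SAP 2.1.1.7 says so only for patients who discontinued, and the explicit missing-mUFC rules cover Weeks 24 and 34. At Week 48 the status is inferred from the all-enrolled denominator and the absence of carry-forward.
- **Non-randomized patients are demonstrably mapped to visits they never have.** Suppose one leaves after Week 26 (Day 183) and has the end-of-treatment visit on Day 211, 28 days later. On the Table 2-1 grid the range is 7 to 21 days and the visit becomes unscheduled Week 28. On that patient's own Table 7-3 schedule the range is 14 to 42 days and it becomes Week 30. The SAP points both to its own tables and to the patient's next visits, so this is an ambiguity rather than a shown error.
- **The bias can be put at several points.** That needs a rate of skipped Week 44 visits, which the documents do not give.

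**Conclusion.** The rule as written gives a wrong time point for a core completer who skipped Week 44. For that patient the error is certain: 56 days against a maximum of 42, and never below 50 within the visit windows. No other visit supplies the Week 48 mUFC, imaging, questionnaire or metabolic data. Each affected patient in control costs 0.7 points on the Week 48 response rate, always downward; the total is unknown.

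The conclusion rests on reading LASTVIS as the last visit attended and on treating a patient with no Week 48 value as not responding within the all-enrolled denominator. It concerns supportive Week 48 results only. The Week 34 primary and Week 24 key secondary endpoints of core completers are untouched. The correction is worth making because the Week 48 estimate and its CI are to be reported and the change is small.

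**What to change.** In SAP 2.1.1.3:

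1. State that Visit 777 of a patient who completed the core phase is mapped to Week 48 when it falls within a stated window of Day 337, whether or not Week 44 was attended. A window of ±14 days, half the planned gap, gives Days 323 to 351. These are the limits the present rule already sets for a completer seen at Week 44 on Day 309 (309 + 14 and 309 + 42).
2. Add Week 48 (Visit 777) to Table 2-1.
3. Keep the LASTVIS rule for patients who discontinued early, and say that it runs on the patient's own schedule (Protocol Table 7-2 if randomized, Table 7-3 if not). Placing these patients by study day instead is not advised: someone who stopped drug after Week 36 and returned near Day 337 would bring off-drug values into the Week 48 summaries.

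The cost is a few lines of SAP text and a small change to the derivation, with no new data. One downside is that core results were already reported in an interim CSR under a separate SAP dated 06-Jul-2018, which is not among the documents. Any Week 48 figure that changes should be noted in the Final CSR with the reason.
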